8.5 Statement of confidentiality

Patients will only be identified by a unique identification number on the study database and data will be anonymised. All data will be treated as confidential.

Each patient's data is linked to their unique identification number.

The patientMpower app is designed with stringent security protocols. The solution is hosted in Google Compute Engine. The security protocols used include:

- app uses a PostgreSQL database (https://www.postgresql.org/) which is backed up nightly
- app is patched regularly to ensure it is maintained against security vulnerabilities
- only certain Internet Protocol (IP) addresses can login to the cloud infrastructure using Secure Shell (SSH) with IP whitelists and public/private key access only
- built-in firewalls
- encrypted data storage
- patientMpower staff access to the PostgreSQL database, and content system is restricted and monitored
- a unique username and password for each user.
- audit and accounting of all access to the system is recorded. In the event of any staff looking at data without proper authorisation, there is an audit trail of what data was viewed
- data transfer between the patient mobile device and cloud server is sent securely via Transport Layer Security (TLS) and the app's cloud infrastructure uses an Extended Validation Secure Sockets Layer (SSL) Certificate issued by Digicert (https://www.digicert.com)
- data on the server is encrypted, only authenticated users can access the server

8.6 **Completion of study**

The study will be complete when 25 patients have completed the 16-week observation period.

If it appears to be unlikely that the target number of patients can be achieved (e.g. because of slow recruitment) a lower target will be set (after discussion and agreement with the investigator).

8.7 **Protocol violations**

All data will be analysed on an intention-to-treat basis without regard to protocol violations.

9 References

10.2 Instructions for performing spirometry at home

Patients will perform one spirometry reading at home once per day (ideally at the same time each day).

Each patient will be supplied with a Spirobank Smart home spirometer (Medical International Research, [name]. www.spirometry.com). This spirometer will automatically upload Peak Expiratory Flow (PEF), Forced Expiratory Volume in 1 second (FEV₁), FVC and FEV1/FVC data directly to the patientMpower app.

10.3 Management and reporting of adverse events/adverse reactions

10.3.1 Definitions of adverse events

An adverse event (AE) is defined as any untoward medical occurrence in a patient or clinical investigation subject administered a medicinal product and which does not necessarily have a causal relationship with this treatment. An AE can therefore be any unfavourable and unintended sign (e.g. an abnormal laboratory finding), symptom, or disease temporally associated with the use of a medicinal product, whether or not considered related to the medicinal product.

An adverse reaction (ADR) is defined as a response to a medicinal product which is noxious and unintended. Response in this context means that a

causal relationship between a medicinal product and an adverse event is at least a reasonable possibility. ADRs may arise from use of the product within or outside the terms of the marketing authorisation or from occupational exposure. Conditions of use outside the marketing authorization include offlabel use, overdose, misuse, abuse and medication errors.

A serious adverse event is defined as any AE which

- results in death,
- is life-threatening,
- requires in-patient hospitalization, or
- prolongation of existing hospitalisation,
- results in persistent or significant disability or incapacity
- is a congenital anomaly/birth defect

Life-threatening in this context refers to a reaction in which the patient was at risk of death at the time of the reaction; it does not refer to a reaction that hypothetically might have caused death if more severe.

Medical and scientific judgement should be exercised in deciding whether other situations should be considered serious reactions, such as important medical events that might not be immediately life threatening or result in death or hospitalisation but might jeopardise the patient or might require intervention to prevent one of the other outcomes listed above. Examples of such events are intensive treatment in an emergency room or at home for allergic bronchospasm, blood dyscrasias or convulsions that do not result in hospitalisation or development of dependency or abuse. Any suspected transmission via a medicinal product of an infectious agent is also considered a serious adverse reaction.

10.3.2 Adverse event and serious adverse event collection and reporting to regulatory authorities and ethics committees.

The investigator shall maintain and keep detailed records of all AEs in their patient records.

The investigator will be responsible for reporting AEs which occur during the conduct of the study to the competent regulatory authorities, accredited Institutional Review Boards and/or Independent Ethics Committee(s) [IRB/IEC(s)] in accordance with the applicable laws and regulations.

10.3.3 Adverse event reporting to Boehringer Ingelheim (for adverse events associated with BI products)

All adverse events associated with use of any Boehringer Ingelheim medicinal products must be reported to Boehringer Ingelheim.

The investigator will report

- 1. all ADRs (serious and non-serious)
- 2. all AEs with fatal outcome
- 3. pregnancies in female subjects and partners of male subjects

which are associated with nintedanib by fax to the BI Unique Entry Point as specified in Safety Data Exchange Agreement using the BI NIS AE report form with the following timelines.

Report to: [name] Boehringer Ingelheim UK and Ireland Pharmacovigilance Department [contact] [contact] E-mail: [contact]

All Serious ADRs and AEs with fatal outcome shall be forwarded immediately [within twenty-four (24) hours or next business day whichever is shorter]. All non-serious ADRs and Pregnancy Monitoring Forms shall be forwarded within seven (7) calendar days

The investigator will carefully assess whether an AE constitutes an ADR using the information below.

Causal relationship of adverse event:

The definition of an ADR implies at least a reasonable possibility of a causal relationship between a suspected medicinal product and an adverse event. An ADR, in contrast to an AE, is characterized by the fact that a causal relationship between a medicinal product and an occurrence is suspected.

Medical judgment should be used to determine the relationship, considering all relevant factors, including pattern of reaction, temporal relationship, dechallenge or re-challenge, confounding factors such as concomitant medication, concomitant diseases and relevant history.

Causality should be assessed for each event as either "yes" or "no". No other variation should be reported.

Intensity of adverse event

The intensity of the AE should be judged based on the following:

- mild: awareness of sign(s) or symptom(s) which is/are easily tolerated
- moderate: enough discomfort to cause interference with usual activity

severe: incapacitating or causing inability to work or to perform usual activities

Pregnancy:

In rare cases, pregnancy might occur in a study. Once a subject has been enrolled into the study, after having taken BI Drug administered for the disease in scope of the study, the investigator must report any drug exposure during pregnancy, which occurred in a female subject or in a partner to a male subject to BI by means of BI Pregnancy Monitoring Form provided.

In the absence of a reportable AE, only the Pregnancy Monitoring Form must be completed, otherwise the NIS AE form is to be completed and forwarded as well within the respective timelines.

Reporting of related Adverse Events associated with any other BI drug The investigator is encouraged to report all adverse events related to any BI drug other than nintedanib according to the local regulatory requirements for spontaneous AE reporting at the investigator's discretion by using the locally established routes and AE report forms. The term AE includes drug exposure during pregnancy, and, regardless of whether an AE occurred or not, any abuse, off-label use, misuse, medication error, occupational exposure, lack of effect, and unexpected benefit.

11 Summary of clinical study protocol modifications

None to date.

STUDY OBJECTIVES	 Characterise longitudinal trends of patient-reported Forced Vital Capacity (FVC) and outcome measures in patients with idiopathic pulmonary fibrosis (IPF). Determine the correlation between patient-reported FVC and outcome measures with clinic-observed measurements. Assess if longitudinal trends in patient-reported FVC predict clinical outcomes. Characterise the acceptability and utility of the patientMpower app from patient and healthcare professional perspectives.
METHODOLOGY	Prospective, open-label, single-arm observational study. Usual care for all patients throughout study.
NUMBER OF SUBJECTS	Total randomised: target = 25

	Actual intention-to-treat: 21. Treated dataset: 20
DIAGNOSIS	Confirmed diagnosis of IPF
MAIN CRITERIA FOR INCLUSION	Age ≥18 years, daily access to smartphone or tablet device, email address, demonstrated understanding of use of patientMpower app and home spirometry, written informed consent
TEST PRODUCT	patientMpower intervention (defined as patientMpower app + home spirometer) used daily + usual care
COMPARATOR PRODUCT	None
DURATION OF OBSERVATION	Sixteen ± eight weeks (corresponding to interval between usual care visits)
END OF STUDY DEFINITION	Date of first usual care visit after baseline visit (typically at sixteen ± eight weeks)
PRIMARY ENDPOINTS	Trend of patient-measured FVC over time. Degree of correlation between patient- measured FVC with clinic- observed measures
SECONDARY ENDPOINTS	Trends of patient-reported outcomes over time. Degree of correlation between patient- reported outcomes with clinic-observed measures. Patient and healthcare professional perspectives on preference for and difficulty using the app and helpfulness in managing IPF. Impact of app on patient self- management of IPF and daily living.
INTERIM ANALYSIS	Analysis of data up to 18 October 2019 to prepare abstract for American Thoracic Society 2020
STATISTICAL METHODS	Descriptive statistics tables prepared for all endpoints

FLOW CHARTS

Flow chart 2: Assessments during observation period

	Baseline (clinic visit)	Install app & pair spirometer	*Daily (patient - reported)	16 (±8) weeks End study (clinic visit) ¹
	day 0	day 0-2	daily	week 16
				(approx.)
Informed consent	Х			
Start of study	Х			
Spirometry, assess dyspnoea	Х			X
Demographic data (include IPF history & medicines history ³)	Х			
Patient training &	Х			
encouragement				
Installation of		Х		
patientMpower app & pair				
spirometer				
Record compliance or changes (IPF medicine) ²	Х		Х	X ³
Patient-measured FVC ²	Х		Х	Х
Record impact of IPF (PROM) ^{4,5}	X ⁴		X ⁵	X ⁴
Patient outcomes (e.g.			Х	
oxygen consumption,				
dyspnoea, pulse oximetry,				
symptoms, vital signs) ⁶				
Utility & acceptability of				Х
app ⁷				
Clinic-reported outcomes				Х
(e.g. exacerbations)				
End of study				Х

¹ End of study visit will be date of usual scheduled clinic visit.

² Reported by patient on patientMpower app every day. Goal is for patient to record one FVC measurement (seated) per day.

³ Clinic to record changes in IPF medication or other medicines prescribed for respiratory conditions.

⁴ Impact of IPF on daily life (Patient Reported Outcome Measure; PROM) to be assessed by clinic team at baseline and end of study visit and recorded on patientMpower app.

⁵ Impact of IPF on daily life (PROM) to be reported by patient on patientMpower app every week.

⁶ Reported by patient as often as possible, ideally each day. These measurements are optional and will only be recorded where practical for the patient.

⁷ Patient and healthcare professional perspective. If patient is withdrawn prematurely, try to capture patient perspective of utility and acceptability of app at time of withdrawal.

List of abbreviations

AE ATS COVID19 ERS EU EWMA FEV1 FVC IPF ITT JRS MIR mMRC pMp PROM	Adverse event American Thoracic Society Coronavirus disease 19 European Respiratory Society European Union Exponentially Weighted Moving Average Forced Expiratory Volume in 1 second Forced Vital Capacity Idiopathic pulmonary fibrosis Intention to treat Japanese Respiratory Society Medical International Research modified Medical Research Council patientMpower application patient reported outcome measure

1. Study protocol

1.1 Protocol

The study protocol was finalised on 11 January 2018 [1].

This was an open-label, single-group observational study of a population of idiopathic pulmonary fibrosis (IPF) patients treated with usual care. There was no control group.

1.2 Protocol amendments

Not applicable.

1.3 Dates of study conduct

The first patient gave informed consent and entered the study on 28 November 2018. In-clinic visits were cancelled at the study centre in March 2020 because of the COVID19 pandemic and the last two patients did not have end-of-study clinic visits. Data for all patients who had completed the study by 30 April 2020 and for the two patients who were still on study on 30 April 2020 are included in this analysis.

1.4 Data management plan

The preparation of listings and tables for analysis is described in the data management plan dated 09 July 2020.

2. Datasets for analysis

2.1 Dataset definitions

The patient populations to be included in the analyses were defined as follows.

- Intention-to-treat dataset: all patients who gave informed consent.
- Treated dataset: all patients in the intention-to-treat dataset who downloaded the patientMpower application (pMp), and used pMp with a MIR Spirobank Smart spirometer at least once.

2.2 Protocol deviations

There was no definition of significant protocol deviations. Data from all patients in the treated dataset were analysed irrespective of adherence to the protocol. The primary analysis was of the treated dataset.

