	address, demonstrated
	understanding of use of
	patientMpower app and home
	spirometry, written informed consent

TEST PRODUCT	patientMpower app (via patient's
	smartphone or tablet device)
DURATION OF OBSERVATION	Sixteen (± eight) weeks
END OF STUDY DEFINITION	Sixteen (± eight) weeks
PRIMARY ENDPOINTS	Trend of patient-measured FVC over
	time.
	Degree of correlation between
	patient-measured FVC with clinic-
	observed measures.
SECONDARY ENDPOINTS	Trends of patient-reported
	outcomes over time.
	Degree of correlation between
	patient-reported outcomes with
	clinic-observed measures.
	Patient and healthcare professional
	perspectives on preference for and
	difficulty using the app and
	helpfulness in managing IPF.
	Impact of app on patient self-
	management of IPF and daily living.
INTERIM ANALYSIS	None planned
STATISTICAL METHODS	Descriptive statistics tables will be
	prepared

FLOW CHARTS

Flow chart 1: Patient recruitment process

Step	Day	Action
1	0 (Baseline)	At a usual care visit to study centre, research team discusses study with patient (face-to-face), confirms patient's understanding of the study processes and willingness to participate. Obtains written informed consent ^A . Study centre conducts usual clinical assessments. Study starts.
2	0 (Baseline)	Study centre advises patientMpower Ltd. of email address of patients who have given consent to participate.
3	0 -2	patientMpower sends information pack (electronic; includes instructions on installation of app) and home spirometer to patient ^B .
4	0 - 2	Patient starts to use patientMpower app and home spirometry as soon as possible after installation of app and pairing of spirometer.

^A Includes explicit consent by patient for patientMpower to know their identity and email address and collect, store and analyse data reported by the patient on the patientMpower app.

^B On request by the patient, patientMpower Ltd can contact patient to offer help with installation of patientMpower application and pairing of spirometer (so that application and spirometer are installed and operating correctly).

Flow chart 2 Assessments during observation period

	Baseline (clinic visit)	Install app & pair spirometer	*Daily (patient -reported)	16 (±8) weeks End study (clinic visit) ¹
	day 0	day 0-2	daily	week 16
				(approx.)
Informed consent	Х			
Start of study	Х			
Spirometry, assess	Х			Х
dyspnoea	N N			
Demographic data (include IPF history & medicines	X			
history ³)	X			
Patient training & encouragement	~			

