5.3. Other variables

Demographic data (date of birth, gender, date of IPF diagnosis, other respiratory conditions, medication prescribed for IPF or respiratory conditions).

Type of smartphone or tablet device (i.e. iPad or Android tablet, iPhone or Android phone)

Engagement of patients with the patientMpower app will be assessed by analysis of the numbers of

- patients asked to take part in the study
- patients who give informed consent to take part in the study.
- consented patients who download the app application to their smartphone or tablet device
- patients who use the app at least once after downloading
- patients who use the app more than once
- frequency of use by each patient
- date intervals between informed consent, download, first use
- date intervals between first and subsequent uses
- frequency of recording FVC at home
- frequency of recording PROM at home
- frequency of recording other measures at home

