6.2.2 Baseline clinic visit

The study procedures and assessments during the observation period at each clinic visit are summarized in flow-chart 2 on page 7.

At a usual care visit to the study centre, the research team will discuss the study with the patient (face-to-face), confirm their understanding of the study processes and their willingness to participate.

Written informed consent will be obtained before any study-specific assessments and before installation of the patientMpower app.

The study starts at this visit.

The patient will be instructed in the correct use of the Spirobank Smart home spirometer and uploading of data to the patientMpower app. The patient's understanding of the patientMpower app, Spirobank Smart home spirometer and the study procedures should be checked before they leave the clinic.

Demographic data, medical history and concomitant therapy for IPF and other respiratory conditions will be recorded.

The following parameters will be assessed and recorded in the clinic records:

- spirometry (to include FVC)
- dyspnoea (e.g. UCSD Shortness of Breath Questionnaire or other measure usually used by the investigator sites) impact of IPF on daily life (using the same PROM as in the patientMpower app)

The study centre will advise patientMpower Ltd that the patient has consented to participate in the study and provide the patient's contact details.

patientMpower Ltd. will send the patient an information pack (via email) and a home spirometer (via regular mail or courier). The information pack will give instructions (including video clips) on how to install the patientMpower app onto your smartphone or tablet device and how to pair the spirometer with the app. During the installation, some information on the patient (e.g. date of birth and gender) will be recorded on the patientMpower app. If necessary, the patient may be loaned a tablet device (like an iPad) which will have the patientMpower app installed. If requested by the patient, patientMpower Ltd. will provide technical support to the patient in downloading the app and pairing with the spirometer.

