6.2.4 End of treatment clinic visit (16 \pm 8 weeks) and follow-up period

The following parameters will be assessed and recorded in the clinic records:

- spirometry (to include FVC)
- dyspnoea (e.g. UCSD Shortness of Breath Questionnaire or other measure usually used by the investigator sites)
- impact of IPF on daily life (using the same PROM as in the patientMpower app)
- medication adherence (if prescribed for IPF)
- changes in or addition of any new medicines for the treatment of IPF (if prescribed)
- exacerbations of IPF since previous visit
- hospitalisations due to IPF since previous visit

The patient and healthcare professional opinion on the usefulness and acceptability of the patientMpower app will be assessed and recorded. (The questions are described in section 5.1.1.2 above.)

7. Statistical methods and determination of sample size

This a pilot study to assess the feasibility of patients with IPF using the patientMpower app including home-based FVC to monitor their health.

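### The SAP names only the treated set for analysis, which fixes app-plus-spirometer uptake at 100%, and its seven-day window rule leaves the N of each FVC correlation unclear

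*SAP*

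**What the plan says.** **Analysis set.** Protocol 8.7, which deals with protocol violations, says: "All data will be analysed on an intention-to-treat basis without regard to protocol violations". The protocol does not define the intention-to-treat set. SAP 2.1 does: it is every patient who consented. The same section defines a treated set, limited to consenters who downloaded the app and used it at least once with the study spirometer, and introduces both sets as populations for analysis. The SAP summary gives 21 and 20 patients. SAP 1.2 reports no protocol amendment. SAP 2.2 keeps treated patients in regardless of adherence and adds: "The primary analysis was of the treated dataset". SAP 5.3 names only the treated set for the planned analysis.

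**Engagement.** Protocol section 7 opens with the purpose: "This a pilot study to assess the feasibility of patients with IPF using the patientMpower app", with home FVC included. Protocol 5.3 lists engagement counts that start before app use, among them "consented patients who download the app application to their smartphone or tablet device" and "patients who use the app at least once after downloading". SAP 4.3 shortens this to the number of users and the frequency of recording, and gives no denominator.

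**Clinic data.** Consent and clinic assessment share the baseline visit; step 1 of protocol Flow chart 1 ends with "Study centre conducts usual clinical assessments. Study starts". Protocol 6.2.2 introduces baseline spirometry, dyspnoea and the impact questionnaire with "The following parameters will be assessed and recorded in the clinic records". The end visit in protocol 6.2.4 adds "exacerbations of IPF since previous visit" and hospitalisations. SAP 5.3 includes clinic-derived parameters and health outcomes in the analysis.

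**Correlation.** SAP 5.3 calculates one home/clinic FVC correlation at baseline and one at end of study. It excludes patients with no home reading in *either* of the two seven-day windows. SAP 1.3 and 2.3 report two patients with no end-of-study clinic visit.

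**The concern.** Entry to the treated set depends on the behaviour that a feasibility pilot sets out to measure. A set chosen for first use of the app with the spirometer cannot show how many consenters reached that step. The protocol's engagement list counts downward from consent, so its natural denominator is the 21. The set also governs clinic-recorded results that need no app use, so one consenter's clinic FVC, exacerbations or hospitalisations could be left out for not having used the device.

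The window rule is a separate matter. The home/clinic FVC correlation is listed among the primary endpoints in the summary of both documents. The word *either* does not settle whether one empty window removes a patient from one coefficient or from both, so a reader cannot tell who enters the baseline correlation.

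**Working it through.** **1. The plan's own figures.** The SAP summary gives 21 consenters and 20 treated. These are observed counts, and the target of 25 is stated to be arbitrary, so there is no power calculation to reproduce. 21 − 20 = 1 consenter outside the treated set, or 1/21 = 4.8%.

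**2. Uptake of app plus spirometer.**
- Treated set: 20/20, by definition.
- Consenters: 20/21 = 95.2%. The exact (Clopper-Pearson) 95% limits are the 0.025 quantile of Beta(20, 2) = 76.2% and the 0.975 quantile of Beta(21, 1) = 99.9%.

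**3. First use of the app alone (protocol 5.3).** The documents do not say whether the 21st consenter used the app without the spirometer. The count is therefore 20/21 or 21/21; for 21/21 the exact lower limit is 0.025^(1/21) = 83.9%.

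**4. Home-FVC recording frequency.** The 21st patient contributes none, so a cohort mean over consenters is the treated-set mean × 20/21. Assumed means of 50%, 70% and 90% become 47.6%, 66.7% and 85.7%.

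**5. Home-FVC trend and the two FVC correlations.** The 21st patient never used the app with the spirometer, so has no home FVC from it, and SAP 5.3 imputes nothing. These results are identical in both sets.

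**6. Clinic-recorded data.** At most 1 of 21 patients (4.8%) is left out. Whether that patient has such data is not stated.

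**7. Window rule.** There are three readings: out of both correlations if one window is empty; out of the affected correlation only; or out only if both windows are empty. The last two give the same N at each time point, because an empty window has no mean to correlate.

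Assume that both patients without an end visit were treated, that their end window counts as empty, and that no clinic FVC is otherwise missing. The number of other empty windows is not given, so rows 2 and 3 are illustrations.

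| Further patients with only the baseline / only the end window empty | Baseline / end N, out of both | Baseline / end N, per window |
|---|---|---|
| 0 / 0 | 18 / 18 | 20 / 18 |
| 1 / 2 | 15 / 15 | 19 / 16 |
| 2 / 4 | 12 / 12 | 18 / 14 |

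Only one consenter is untreated, so at least one of the two patients was treated. If only one was, the first-row baseline N is 19 against 20.

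**8. Precision.** The Fisher-z standard error is 1/√(n − 3): 0.243 at n = 20 and 0.258 at n = 18, a ratio of √(17/15) = 1.06. At an assumed r of 0.90 the 95% interval is 0.760–0.960 at n = 20 and 0.747–0.962 at n = 18. In the third row the contrast is n = 18 against n = 12 (0.674–0.972), a standard-error ratio of √(15/9) = 1.29.

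**The case against.** The strongest reply on the set is that protocol 8.7 concerns protocol violations in a single-arm observational study and never defines intention-to-treat. Its practical content, keeping patients regardless of adherence, survives in SAP 2.2. That is fair as far as it goes. But SAP 2.2 applies it only inside the treated set, and entry to that set is itself conditional on use. The mismatch is with the SAP's own definition of intention-to-treat as all consenters.

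Three further replies stand. Calling the treated set primary leaves room for other analyses, and the two files not supplied (Appendix 1 and the data management plan) could hold one on the 21. Nobody has claimed 100% uptake: the SAP summary prints 21 and 20 together, so 20/21 can already be read off. App-plus-spirometer uptake is also not itself an item in protocol 5.3, whose app-only first-use count may be 21/21.

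On the window rule, two of the three readings give per-window numbers, and separate correlations at each time point point the same way. For the two patients without an end visit there is no clinic FVC to pair, so they are outside the end-of-study correlation on any reading; only their place in the baseline correlation is open.

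A reader might infer that choosing the treated set biases the primary FVC result. The documents do not support this, because the excluded consenter has no home FVC to contribute. A reader might also infer that the rule certainly drops patients from both correlations; the text is ambiguous, not explicit.

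**Conclusion.** The point holds and is minor. In the supplied text the SAP moves from the protocol's intention-to-treat principle to a set selected on use, without explanation and without assigning any analysis to the 21 consenters. The effect is confined to engagement denominators (20/20 by construction against 20/21 = 95.2%) and possibly one patient's clinic-recorded data.

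The window rule needs a definite reading. From the two patients without an end visit alone, the baseline N is 20 or 18. This assumes that both were treated and that a window with no visit to anchor it counts as empty. That change barely moves the interval, but it would be wrong to infer that the rule's effect is small overall: the number of other empty windows is unknown, and the illustrations show the gap can widen.

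**What to change.** 1. Report download, first use, repeat use and recording frequency (protocol 5.3) with the 21 consenters as denominator. Include the 21st patient in clinic-recorded outcomes where data exist. Keep the treated set for home FVC, and state this as a departure from protocol 8.7.
2. In SAP 5.3, apply the home-reading requirement separately at baseline and at end of study, so that each correlation uses every patient with a clinic FVC and a home reading in that window. Report N for each.

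The cost is a few lines of SAP text and light re-tabulation from existing app and clinic records. The number who downloaded the app is not given in the SAP, so that step depends on what was recorded. The app-plus-spirometer uptake figure becomes slightly less favourable.
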